1.2 SCHEME

1.3 SCHEDULE OF ACTIVITIES

	Screening / Selection	Assessment 1	Visit 1: Carotid ultrasonography + laboratory analyses	Randomization	Visit 2: Intervention session	Visits 3 to 15: Biweekly telephone contacts	Assessment 2 (6 months)	Assessment 3 (18 months)	End of study
Assessment of inclusion/exclusion criteria	X								
Signing of informed consent		X							
Collection of sociodemographic variables		X							
Review of medical history and current medication		X						X	
Anthropometric measurements (weight, height, BMI, waist circumference)		X					X	X	
Health-related quality of life questionnaire (SF-36)		X					X	X	
Dietary questionnaire (24-hour recall)		X				X	X	X	
Physical activity questionnaire (IPAQ)		X					X	X	
Laboratory analyses (HbA1c, glucose, insulin, lipids, etc.)			X				X	X	
Imaging studies (Carotid ultrasonography)			X				X	X	
Randomization				X					
Adverse event recording		X					X	X	X
Telephone follow-up for clinical status						X			

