- **SF-36:** This is a generic scale that provides a health status profile and is applicable both to patients and to the general population. The 36 items of the instrument cover the following domains: Physical Functioning, Role Physical, Bodily Pain, General Health, Vitality, Social Functioning, Role Emotional, and Mental Health. For each domain, items are coded, aggregated, and transformed into a scale ranging from 0 (worst health status for that dimension) to 100 (best health status) (*Alonso et al., 1995*).

e) Medication consumption

- **Defined Daily Dose (DDD) by active substance:** DDDs of the active substances consumed will be classified according to ATC7. Each ATC classification has a defined daily dose based on international standards, which determine the recommended maximum daily amount for the approved indication of the active substance (*WHOCC, n.d.*).

Control variables and management of T2DM

Patients will be assessed during each follow-up telephone visit throughout the intervention, at the end of the intervention, and one year after its completion. For the control group (Group B), episodes will be identified through records in the electronic health record system (eCAP).

- **Number of hypoglycemia episodes:** Episodes of hypoglycemia detected by patients through capillary blood glucose levels and/or recorded in eCAP during the intervention (plasma glucose <60 mg/dl).
- **Number of symptomatic hyperglycemia episodes:** Episodes of hyperglycemia recorded in eCAP during the intervention (plasma glucose >350 mg/dl accompanied by compatible symptoms such as general malaise, nausea, asthenia, among others).

- **Total number of healthcare visits:** Annual contacts with the healthcare system including Primary Care (physicians and nursing), Specialized Care, and Emergency Care.
- **Number of diabetes-related emergency episodes:** Emergency visits related to diabetes during the intervention period.

Recruitment

Through the internal registry of the Primary Care Clinical Station (eCAP), patients with a diagnosis of Type 2 Diabetes Mellitus (T2DM) from each primary care center (CAP) will be identified. Potential participants will be validated by a physician not involved in the intervention, in order to exclude false positives due to registry errors and to confirm inclusion and exclusion criteria.

Randomization will be performed by stratifying according to the characteristics defined in section 6.2. Study Design.

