8.2 SAFETY ASSESSMENTS

The CREDOenAP program intervention is considered a low-risk intervention due to its behavioral nature. It does not involve the use of any drugs or invasive procedures. However, several measures have been planned to assess and ensure the safety of participants in the intervention:

- Adverse event monitoring: During the scheduled follow-up sessions within the intervention, the professional responsible for conducting the sessions will also be in charge of identifying and reporting any adverse events. Any signs of physical or emotional discomfort or change will be recorded. Subsequently, the event will be evaluated to determine its severity and the appropriate response protocol.

In the event of an adverse event, it will be assessed to determine its severity and whether it requires additional medical attention or poses a risk to the participant's safety. If necessary, the participant will be referred to receive specific treatment. Finally, their continuation in the intervention will be evaluated.

All identified adverse events will be documented in the study's official registry.

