8.3.4 TIME PERIOD AND FREQUENCY FOR EVENT ASSESSMENT AND FOLLOW-UP

All procedures and events occurring in the patients will be recorded. These records will be made every 15 days, coinciding with the scheduled follow-up visits of the intervention. The classification of the type of event will be carried out by a clinician external to the intervention, who can independently assess the severity of the event.

All adverse events occurring at any time after obtaining informed consent will be recorded, up to 7 days after the study completion for mild adverse events, or up to 30 days for serious adverse events. At each study visit, the investigator will inquire about the occurrence of adverse or serious adverse events since the last visit. Events will be followed up to obtain information on outcomes until resolution or stabilization.

For each identified event, the symptoms, onset date, duration of symptoms (if applicable), and any required treatment will be documented. Any deterioration or change in the patient's baseline conditions, both related to T2DM and other comorbidities, will also be recorded as an adverse event.

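### Hypoglycaemia and mild adverse events are sought about every two weeks in Group A but not in Group B, so a reported between-arm comparison of them would partly measure detection

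*Protocol*

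**What the plan says.** **Hypoglycaemia (Section 8.1, control variables and management of T2DM).** The general rule is "Patients will be assessed during each follow-up telephone visit throughout the intervention, at the end of the intervention, and one year after its completion". For controls it is "For the control group (Group B), episodes will be identified through records in the electronic health record system (eCAP". The definition covers "Episodes of hypoglycemia detected by patients through capillary blood glucose levels and/or recorded in eCAP during the intervention", with a threshold of 60 mg/dl.

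**Symptomatic hyperglycaemia (same section).** The definition is "Episodes of hyperglycemia recorded in eCAP during the intervention", above 350 mg/dl with symptoms. It makes no distinction by arm.

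**Adverse events.** Section 8.2 states that during follow-up sessions "the professional responsible for conducting the sessions will also be in charge of identifying and reporting any adverse events". Section 8.3.4 adds "These records will be made every 15 days, coinciding with the scheduled follow-up visits of the intervention", and also has the investigator ask about events at each study visit. Section 8.3.5 names two possible recorders, the caller or the examiner at scheduled examinations, and sends each event to both the study registry and the patient's shared medical record.

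**Contacts.** The schedule in Section 1.3 has a column "Visits 3 to 15: Biweekly telephone contacts". Its row "Adverse event recording" is marked at the three assessments and at end of study, but not in that column. Section 4.1 limits research-team involvement with Group B to data collection at baseline and at the end of each phase.

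**Analysis.** Section 9.4.4 (safety analyses) is marked not applicable. Section 9.4.8 lists safety outcomes by participant.

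**The concern.** A low reading that a participant takes at home and treats without seeking care can be counted in Group A, because someone telephones about two weeks later and asks. In Group B the same reading counts only if it reached eCAP. A minor adverse event in Group A is asked about within about two weeks; in Group B it must be remembered until the 6-month assessment.

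These counts are of interest. Section 2.3.2 names avoidance of hypoglycaemia as an expected benefit, and Section 8.3.1 lists hypoglycaemia and hyperglycaemia among the adverse events that may occur. Sections 10.1.6 and 10.1.7 provide for no independent safety board and no external monitoring. If the arms are set side by side, under-detection in controls could produce an apparent excess in Group A or hide a real reduction. The analysis cannot repair this later, because control episodes that nobody asked about are not in the data.

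**Working it through.** The protocol states no figure on this point, so there is nothing to reproduce. The check compares the routes of detection and then illustrates the consequence.

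**Step 1: contacts up to month 6.** Visits 3 to 15 make 15 − 3 + 1 = 13 calls, which agrees with 26 weeks / 2 = 13. Group B has 0 calls. Both arms attend the 6- and 18-month assessments. Neither arm has calls scheduled after month 6, so the difference arises in the intervention period.

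**Step 2: routes by type of event.**

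| Event | Group A | Group B | Same rule? |
|---|---|---|---|
| Hypoglycaemia | Calls, patient-detected readings, eCAP | eCAP; no stated route for patient-detected readings | No |
| Mild adverse events | Search every 15 days, plus assessments | Assessments | No |
| Symptomatic hyperglycaemia | eCAP | eCAP | Nominally yes |
| Diabetes-related emergency visits | No arm-specific rule in the definition | eCAP | Largely |

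The blinding of evaluators at the end of Section 8.1 covers tests and questionnaires. It does not cover events found on calls.

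**Step 3: leakage into the record.** Section 8.3.5 puts every identified adverse event into the shared medical record, and Sections 10.1.8 and 10.1.9.1 describe eCAP as the shared electronic health record. On that reading, a Group A event found on a call becomes an eCAP entry. Restricting the comparison to eCAP would therefore not make it even. This is also the indirect way in which hyperglycaemia counts could be affected.

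**Step 4: illustration.** Observed risk = true risk × detection probability. With equal true risks, the observed risk ratio equals the ratio of detection probabilities. Assumptions, none of them in the protocol: true risk 20% in both arms and detection 0.9 in Group A. The arm size of 60 is from Section 9.2.

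| Assumed detection in B | Observed risk A vs B | Expected cases A vs B | Observed ratio | Chance of a nominally significant excess in A |
|---|---|---|---|---|
| 0.6 | 0.18 vs 0.12 | 10.8 vs 7.2 | 1.5 | about 15% |
| 0.45 | 0.18 vs 0.09 | 10.8 vs 5.4 | 2.0 | about 30% |
| 0.3 | 0.18 vs 0.06 | 10.8 vs 3.6 | 3.0 | about 53% |

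The last column uses the normal approximation for two proportions at two-sided 5%. For the middle row, the standard error under the null is √(2 × 0.135 × 0.865 / 60) = 0.0624 and under the alternative √((0.18 × 0.82 + 0.09 × 0.91) / 60) = 0.0618. Then Φ((0.09 − 1.96 × 0.0624) / 0.0618) ≈ 0.30. At a true risk of 10% the three chances are about 9%, 16% and 28%; at 30% they are about 22%, 45% and 73%. With equal detection the ratio is 1.0 and the test rejects 5% of the time in total.

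Masking works the same way: a true ratio of 0.5 would appear as 0.5 × 0.9 / 0.45 = 1.0.

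**Step 5: internal conflicts.** Sections 8.2 and 8.3.4 place adverse event recording at the biweekly contacts, while the Section 1.3 schedule does not mark it there. The text of Section 8.1 has patients assessed up to one year after the intervention, yet counts episodes during the intervention; the table in Section 8.1 marks episodes at follow-up visits and month 6, not at month 18.

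**The case against.** The strongest reply is that the protocol plans no such comparison. Section 9.4.4 is marked not applicable, and episode counts are neither objectives nor endpoints in Section 3 nor listed in Section 9.4.3. This stands: the point applies only to a comparison that someone reports. Episodes are nevertheless collected in both arms and safety outcomes are tabulated, so the collection rule matters.

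A reader might infer more than the text supports in four ways:

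- **Hyperglycaemia is counted by two rules.** It is not. Its definition is eCAP-based in both arms, and only the leakage in Step 3 touches it.
- **Controls are never asked about adverse events.** They are, at the shared assessments (Sections 1.3, 8.3.4 and 8.3.5). What they lack is the biweekly search.
- **Every safety comparison is biased.** Deaths, admissions and emergency visits are likely to reach the record in either arm.
- **The intervention will look less safe by a known factor.** The ratios in Step 4 only restate assumed detection rates. The direction for adverse events is not certain either, because the unblinded person who delivers the sessions also identifies the events and could under-report them.

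It could also be said that the calls serve participants' safety and should stay. That is right, and the fix removes none of them.

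**Conclusion.** The point holds in limited form. Detection of hypoglycaemia differs by arm in the protocol's own words, and the biweekly adverse event search is tied to visits that only Group A has. Nothing elsewhere in the document evens this out. A reported between-arm comparison of hypoglycaemia or mild adverse events would therefore be distorted by differential detection.

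The size cannot be derived from the protocol. The illustrative ratios of 1.5 to 3.0 rest wholly on the assumed detection of 0.9 against 0.6 to 0.3. The primary endpoint is not affected. The change should be made because it concerns data collection, which an analysis plan cannot correct afterwards.

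**What to change.** 1. State in Sections 8.1 and 8.3.4 that between-arm summaries of hypoglycaemia and adverse events use the same sources and the same stated window in both arms: (a) one structured question, including self-measured hypoglycaemia, put to both arms at the existing 6- and 18-month assessments; and (b) eCAP entries that did not originate from a study call.
2. Record the origin of each eCAP entry, because Section 8.3.5 sends call-detected events into the shared record.
3. Report call-detected events separately and descriptively, for Group A only.
4. Reconcile the Section 1.3 schedule with Sections 8.2 and 8.3.4 on adverse event recording at telephone visits.
5. Reconcile the Section 8.1 text with its table on whether episodes are recorded at 18 months and over which period they count.

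**Cost.** Protocol wording, one standard question at visits both arms already attend, and one extra data field. Fewer mild events enter the comparison, and recall at 6 and 18 months is less complete than biweekly inquiry. Some imbalance may remain, since Group A participants who have been asked repeatedly may remember more.

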As part of the cardiovascular risk factor assessment, three ultrasound examinations of the carotides will be performed during the study: at baseline, at the end of the intervention, and 12 months after the completion of the intervention.

	1st Examination and Sample Collection T0 (Baseline / Start of Intervention)	Follow-up Visits	2nd Examination and Sample Collection T-6 months (End of Intervention)	3rd Examination and Sample Collection T-18 months (12 months after End of Intervention)
Questionnaires and Assessment Scales				
24-Hour Recall	X	X	X	X
SF36	X		X	X
IPAQ	X		X	X
Tobacco consumption	X	X	X	X
Alcohol consumption	X	X	X	X
Circadian cycle	X	X	X	X
Physical Examination (Anthropometric Measurements)				
Weight	X	X	X	X
Height	X			
Abdominal circumference	X	X	X	X
Blood Analysis				
Complete blood count ^a (CBC ^a)	X		X	X
C-Reactive protein ^a (CRP ^a)	X		X	X
HbA1c	X		X	X
Creatinine ^a	X		X	X
Glomerular filtration rate ^a (GFR ^a)	X		X	X
Aspartate Aminotransferase (AST)	X		X	X

Alanine Aminotransferase (ALT)	X		X	X
Gamma-Glutamyl Transferase (GGT)	X		X	X
Alkaline Phosphatase ^a (ALP ^a)	X		X	X
Amylase ^a	X		X	X
Total Blood Protein ^a	X		X	X
Electrolyte Panel ^a	X		X	X
Calcium ^a	X		X	X
Phosphate ^a	X		X	X
Lipid Profile (Total Cholesterol, HDL, LDL, Triglycerides, Apo B100)	X		X	X
Basal C-Peptide ^a	X		X	X
Anti-GAD Antibodies (GAD Ab)	X			
TSH ^a	X		X	X
Free T4 ^a (Free Thyroxine ^a)	X		X	X
CA 19.9. ^a	X		X	X
Urine Analysis				
Urine Sediment ^a	X		X	X
Albumin/Creatinine Ratio ^a	X		X	X
Imaging Test (Ultrasound)				
Carotid ultrasonography	X		X	X
Type 2 Diabetes Management and Monitoring				
Hypoglycemia episode(s)		X	x	
Hyperglycemia episode(s)		X	x	

^a Parameters to assess the participant's general health status. These parameters are included in the routine monitoring of a person with type 2 diabetes (T2DM).

^b Only in cases of a discordant relationship between HbA1c values and plasma glucose.

Examinations, laboratory tests, imaging studies, and questionnaires will be conducted at the patient's primary care center (CAP Barceloneta or CAP Larrard) by healthcare personnel (physician/nurse according to the test and training) during regular working hours. Blinding will be implemented for the evaluators, as all tests and questionnaires will be carried out by personnel not

involved in the research team and not responsible for delivering the intervention, with no knowledge of the participant's assignment to group A or B in the study.

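### Section 8.1 promises a one-year follow-up of the diabetes control variables, but three of the four definitions, and the table rows for both episode counts, stop at month 6

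*Protocol*

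**What the plan says.** The lead-in to the block on control variables and management of T2DM in Protocol section 8.1 sets the assessment times: "Patients will be assessed during each follow-up telephone visit throughout the intervention, at the end of the intervention, and one year after its completion". Control-arm episodes are to be found in eCAP, the electronic health record.

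Four variables follow, each with its own window:

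- **Hypoglycaemia (plasma glucose <60 mg/dl):** "Episodes of hypoglycemia detected by patients through capillary blood glucose levels and/or recorded in eCAP during the intervention".
- **Symptomatic hyperglycaemia (>350 mg/dl with symptoms):** "Episodes of hyperglycemia recorded in eCAP during the intervention".
- **Total healthcare visits:** "Annual contacts with the healthcare system including Primary Care", together with specialised and emergency care.
- **Diabetes-related emergencies:** "Emergency visits related to diabetes during the intervention period".

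Section 4.1 sets the intervention at 6 months, with a final assessment at month 18. In the assessment table of section 8.1, the two episode rows are marked at the follow-up visits and at 6 months. Their 18-month cells are empty.

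**The concern.** The lead-in calls for a month-18 assessment, but three of the four variables have no window that it could fill. Staff who follow the lead-in will collect months 6–18. Staff who follow the definitions or the table will not.

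The period in doubt matters for safety. Section 2.3.1 names hyperglycaemia in people who stop drugs, should long-term adherence fail, as the long-term risk, and says close monitoring during the study will minimise it. Biweekly contact ends at month 6. The 18-month remission endpoint asks for at least 9 months without antidiabetic medication. If those months run up to the month-18 visit, participants in remission are off drugs from month 9 (18 − 9) at the latest, wholly inside the uncounted year. Under the stated rule, an episode in month 9 or month 14 does not enter the counts.

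**Working it through.** The protocol states no figure to reproduce here. The check is a comparison of texts plus two counts.

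**1. Lead-in against definitions (section 8.1)**

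| Variable | Window in its definition | Can hold data from months 6–18? |
|---|---|---|
| Hypoglycaemia | During the intervention | No |
| Symptomatic hyperglycaemia | During the intervention | No |
| Total healthcare visits | Annual | Yes |
| Diabetes-related emergencies | Intervention period | No |

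Three of four are limited to months 0–6. Time omitted: 18 − 6 = 12 months, and 12/18 = 67% of participant follow-up. This is a share of calendar time, not of events.

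The month-18 assessment could be read as a look back at months 0–6. That is strained, because the end-of-intervention assessment already covers those months. In the hypoglycaemia definition, the limit could be read as applying only to the eCAP records, but the empty 18-month cell in that row supports the narrow reading.

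**2. Rows of the 8.1 assessment table**

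- Total rows: 6 questionnaires + 3 physical + 20 blood + 2 urine + 1 imaging + 2 episode rows = 34.
- Marked at 6 months: 34 − 2 (height, anti-GAD) = 32.
- Of those, also marked at 18 months: 32 − 2 (hypoglycaemia, hyperglycaemia) = 30.

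The only two rows marked at month 6 but not at month 18 are the episode rows. A fault in reading the PDF table is unlikely, since both rows show the same pattern and it agrees with the written definitions. The table has no row for healthcare visits or emergencies, so it says nothing about those two.

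**3. What else covers months 6–18**

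- Section 8.3.1 lists hypo- and hyperglycaemia among the possible adverse events.
- Section 1.3 schedules adverse-event recording at 18 months.
- Section 8.3.4 has each visit ask about events since the last one and document onset dates.
- None of these carries the 60 or 350 mg/dl threshold.
- Section 9.4.4 gives safety analyses as not applicable, and section 9.4.8 provides individual listings only.

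A late episode can therefore be logged as a dated adverse event, but it does not enter the threshold-based count. The number of episodes missed cannot be estimated, because the protocol gives no event rate.

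**The case against.** The strongest reply is that the operative text agrees with itself. Three definitions and both table rows use the same window, and the lead-in is a loose umbrella sentence that still has content at month 18 through the annual visit count. Counting acute episodes while drugs are being adjusted under close contact is a defensible choice. Deleting the one-year phrase for these variables would also remove the conflict.

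Loss of glycaemic control after the programme is also seen by other routes. HbA1c is measured at month 18, section 6.5.1 records the date, type and dose of rescue drugs, and section 8.3.4 records any T2DM-related deterioration as an adverse event. What is missing is a count of acute episodes.

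Finally, ascertainment of hypoglycaemia differs between arms even in months 0–6. Control-arm episodes come from eCAP only, while intervention participants are also asked at the calls and can report their own capillary readings. Extending the window would not extend an already comparable measure.

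Much of this stands. The long-term risk is not unobserved, and the finding rests on no planned efficacy result. But the umbrella reading still leaves conflicting collection windows in one section, and none of the other routes gives a threshold-based comparison of the arms for months 6–18. The difference in ascertainment is a reason to use one source for both arms in that period and to report it separately. It is not a reason to leave the year out.

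**Conclusion.** The concern holds, as a minor point. Section 8.1 assigns a month-18 assessment to variables of which three out of four are defined to stop at month 6, and its table leaves both episode rows unmarked at month 18. As defined, the counts leave out 12 of 18 months in both arms, the period in which the risk named in section 2.3.1 mainly falls.

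This rests on reading the limiting phrases as the 6-month intervention of section 4.1, and on the table marks as they appear in the extracted text. No primary or secondary endpoint and no planned efficacy analysis uses these counts, so the consequence is confined to safety data.

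**What to change.** 1. In section 8.1, define the counts of hypoglycaemia, symptomatic hyperglycaemia and diabetes-related emergencies from randomisation to month 18, reported separately for months 0–6 and 6–18.
2. In the 8.1 assessment table, mark both episode rows at 18 months.
3. At month 18, extract the episodes and diabetes-related emergencies of months 6–18 from eCAP, with the same thresholds and in the same way in both arms. eCAP is already the control-arm source.

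The cost is the wording of three definitions, two table marks and one extraction for up to 120 participants, with no new visits or tests. The downside is some extraction time, and eCAP alone will miss home-detected hypoglycaemia that was never recorded, in both arms. That is one reason to keep the two periods separate.

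If the sponsor does intend months 0–6 only, the lead-in should instead drop the one-year assessment for these three variables. That removes the contradiction but leaves the follow-up year without these counts, so the wider window is preferable.
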